4.1 Study treatment grouping

This study is a prospective, open-label, double-arm, Phase II clinical trial that includes a neoadjuvant treatment group using the mFOLFOX6 regimen and a neoadjuvant treatment group combining the mFOLFOX6 regimen with Citrus Flavonoid Tablets (Aimalang). The study aims to enroll patients with locally advanced rectal cancer who are in clinical stage I, II, or III. Endoscopic biopsy specimens will be collected for YWHAB immunohistochemical testing to identify patients with high YWHAB expression in locally advanced rectal cancer. These patients will then be randomly assigned to either the mFOLFOX6 treatment group or the mFOLFOX6 combined with Citrus Flavonoid Tablets (Aimalang) treatment group for neoadjuvant therapy. The mFOLFOX6 regimen involves 4-6 cycles before surgery and 6-8 cycles after surgery, with each cycle lasting 14 days: on day 1, 85 mg/m² of oxaliplatin is administered intravenously over 180 minutes; on day 1, 400 mg/m² of leucovorin is administered intravenously over 120 minutes; and on day 1, 2400 mg/m² of 5-fluorouracil is administered continuously intravenously for 46 hours. The Citrus Flavonoid Tablets (Aimalang) treatment regimen involves taking 500mg of Citrus Flavonoid Tablets (Aimalang) orally three times daily, with doses given on days 1-14 of each 14-day cycle.

This trial allows for dose adjustments. Patients who experience disease progression during neoadjuvant therapy may stop the study treatment and directly undergo surgery or follow local guidelines. If a patient cannot tolerate the planned 6 cycles of neoadjuvant therapy, early surgery can be considered. Any patient who has received another anticancer regimen before surgery will stop the study treatment and be managed according to local guidelines. The postoperative

treatment for both groups is determined by the investigator, which may include continuing the mFOLFOX6 regimen combined with Citrus Flavonoid Tablets (Aimalang). It is important to note that all patients in the control group are prohibited from taking Citrus Flavonoid Tablets (Aimalang) without authorization during the trial. If a patient needs to take this medication for any reason, they should consult their primary physician, who will decide whether to use an alternative or discontinue the patient's participation in the trial.

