The main efficacy indicator of this study was the proportion of patients in each treatment group who achieved tumor downstaging (ypTNM 0-I stage), and the secondary efficacy indicators were the proportion of patients with complete pathological remission, 3-year disease-free survival (DFS), overall survival time (OS) and tumor regression grade TRG.

6.2 Evaluation criteria of effectiveness:

This study evaluated the proportion of patients with YWHAB high expression locally advanced rectal cancer who achieved tumor downstaging (ypTNM 0-I stage) in neoadjuvant treatment with mFOLFOX6 combined with citrus flavonoid tablets (Aimalang).

- (1) Downstaging rate of tumor (ypTNM 0-I stage): the proportion of patients with locally advanced rectal cancer who received mFOLFOX6 or mFOLFOX6 combined with citrus flavonoid tablets (Aimalang) as neoadjuvant chemotherapy, and the proportion of patients with postoperative pathological stage of ypTNM 0-I stage in surgical specimens.
- (2) The degree of pathological remission is defined as follows: ① Complete Remission (CR): All tumor target lesions have disappeared, no new lesions have appeared, and tumor markers are normal, lasting at least 4 weeks. ② Partial Response (PR): The sum of the maximum diameters of tumor target lesions has decreased by at least 30%, lasting at least 4 weeks. ③ Stable Disease (SD): The sum of the maximum diameters of tumor target lesions has not decreased by more than PR, or increased by less than PD. ④ Disease Progression (PD): The sum of the maximum diameters of tumor target lesions has increased by at least 20%, or new lesions have appeared.

Subjects who did not meet the primary endpoint criteria are included in the denominator but not in the numerator.

- (3) When determining the disease-free survival (DFS), clinical deterioration without clear evidence of disease progression according to the RECIST 1.1 criteria is not considered a disease progression. For subjects who died without prior reported disease progression, it is considered that the disease progressed at the time of death. Subjects who have neither experienced disease progression nor died will be censored at their last evaluable tumor evaluation date. Independent central imaging review will be conducted to confirm the independent central imaging service provider of the subject, which will receive all images from the research center and assess the subject's disease progression according to the RECIST 1.1 criteria.

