8.1 Analysis of population

- Informed Consent Set ICS: This analysis set will include all subjects who have signed an informed consent form.
- Intention-to-treat (ITT) analysis set: According to the principle of intention-to-treat analysis, all patients who were randomly assigned to the group at the time of randomization were analyzed according to the group into which they were assigned. This analysis set is the main analysis set for

efficacy endpoints.

- The Full Analysis Set (FAS) is defined as the group of all participants who were enrolled and received at least one dose of the study drug, following the intention to treat (ITT) principle. In analyses based on the FAS, participants are included according to their assigned group at enrollment, regardless of the actual treatment they received;
- In line with the protocol analysis set (Per-Protocol Set, PPS), ITT patients who did not experience significant protocol deviations that affected the efficacy assessment were included. The PP population was used for sensitivity analysis of the primary and key secondary efficacy endpoints.
- Safety set (Safety Set, SS): Will include all subjects who have received at least one study drug treatment. The safety set is the primary population for safety analysis.

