8.3 Efficacy analysis and statistical methods

For the proportion of patients in each treatment group who achieved tumor downstaging (ypTNM 0-I stage), the proportion of participants with pathological complete remission, and the tumor regression grading (TRG), statistical analysis was conducted using mean values and standard deviations. For the three-year disease-free survival rate and overall survival time, Kaplan-Meier curves were plotted, and the 95% confidence interval for the median time was calculated using the Brookmeyer Crowley method. The Log-rank test was used to compare differences between groups, and the hazard ratios (HR) for each endpoint were

estimated using the Cox proportional hazards model, exploring the impact of factors other than treatment on these endpoints. Additionally, the number and percentage of cases that occurred at each endpoint, as well as the number and percentage of censored cases, were calculated and categorized by censoring reason.

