8.5 Sample size determination

This study primarily focuses on the rate of tumor downstaging (ypTNM 0-I stage) in each treatment group. Based on current data, after

neoadjuvant chemotherapy with mFOLFOX6, approximately 35% of locally advanced rectal cancer patients achieve tumor downstaging (ypTNM 0-I stage). Among these, about one-third (n=90) of YWHAB high-expressing locally advanced rectal cancer patients achieved a tumor downstaging rate of about 25%, while about two-thirds (n=90) of YWHAB low-expressing locally advanced rectal cancer patients achieved a tumor downstaging rate of about 43%. It is estimated that the tumor downstaging rate for YWHAB high-expressing patients receiving mFOLFOX6 combined with citrus flavonoid tablets (Aimalang) neoadjuvant chemotherapy is 40%, with a significance level of 0.05, an efficiency of 0.8, and a dropout rate of 10%. The sample size was estimated to be 236 using PASS V15 software.

Ethical considerations

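### The sample size of 236 does not follow from its stated inputs; with 10% dropout they give 330–338 (two-sided) or 260–268 (one-sided)

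*Combined protocol and SAP*

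**What the plan says.** Section 8.5 bases the size on the primary endpoint, tumour downstaging to ypTNM 0-I. It takes 25% on mFOLFOX6 alone in YWHAB-high patients and expects 40% with the tablets added. It continues: "with a significance level of 0.05, an efficiency of 0.8, and a dropout rate of 10%. The sample size was estimated to be 236", citing PASS V15. I read the word efficiency as power. The section does not give the test, its sidedness or the allocation ratio. Nor does it say whether 236 is a total or per arm, or randomised or evaluable.

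The other sections do not fill the gap:

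- Section 4.1 randomises without a ratio: "These patients will then be randomly assigned to either the mFOLFOX6 treatment group or the mFOLFOX6 combined with Citrus Flavonoid Tablets".
- Section 8.3 says of the downstaging proportion that "statistical analysis was conducted using mean values and standard deviations". The log-rank test there applies to DFS and OS, so no between-group test is named for the primary endpoint.
- Section 8.1 makes ITT the main efficacy set, in which "all patients who were randomly assigned to the group at the time of randomization were analyzed" as assigned.
- Section 6.2 adds: "Subjects who did not meet the primary endpoint criteria are included in the denominator but not in the numerator". It does not say whether this covers patients with no ypTNM stage.
- Section 4.1 also says: "If a patient cannot tolerate the planned 6 cycles of neoadjuvant therapy, early surgery can be considered". Some patients who stop early will therefore still have a stage.

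For the background rates, section 8.5 says that "about one-third (n=90) of YWHAB high-expressing locally advanced rectal cancer patients achieved a tumor downstaging rate of about 25" percent and "about two-thirds (n=90) of YWHAB low-expressing locally advanced rectal cancer patients achieved a tumor downstaging rate of about 43" percent, with about 35% overall.

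**The concern.** The sentence in section 8.5 presents 236 as the product of five numerical inputs. A standard calculation from those inputs gives a clearly larger number whichever sidedness is assumed, so the gap is more than an omitted detail.

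This is the plan's only size justification for the primary endpoint, and it carries a claim of 80% power. If the trial randomises 236 and loses the 10% it expects to lose, it has less power than the ethics committee and readers have been told. At 63–65%, a real improvement from 25% to 40% would be missed more than one time in three, and a null result could be taken as evidence against the combination.

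**Working it through.** **Inputs, all from section 8.5:** p1 = 0.25, p2 = 0.40, alpha 0.05, power 0.80, dropout 10%. **Assumptions where the plan is silent:** 236 is the total, allocation is 1:1, and the test is a two-proportion z-test without continuity correction. Both sidednesses were tried.

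**1. Size before dropout**

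Unpooled, per arm: n = (z_alpha + z_power)² × [p1(1−p1) + p2(1−p2)] / (p2−p1)².
The variance term is 0.1875 + 0.24 = 0.4275, and 0.4275 / 0.15² = 19.

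- Two-sided: (1.960 + 0.842)² × 19 = 149.13, so 150 per arm, 300 in total.
- One-sided: (1.645 + 0.842)² × 19 = 117.47, so 118 per arm, **236** in total.

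Pooled, with mean rate 0.325: n = [z_alpha √(2 × 0.325 × 0.675) + z_power √0.4275]² / 0.15².

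- Two-sided: 151.87, so 152 per arm, 304 in total.
- One-sided: 119.51, so 120 per arm, 240 in total.

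The plan's figure is thus reproduced only by the one-sided unpooled formula with no dropout allowance.

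**2. Size after 10% dropout**

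| | Before dropout | × 1.1 | ÷ 0.9, rounded up per arm |
|---|---|---|---|
| Two-sided, unpooled | 300 | 330 | 334 |
| Two-sided, pooled | 304 | 334.4 | 338 |
| One-sided, unpooled | 236 | 259.6, so 260 | 264 |
| One-sided, pooled | 240 | 264 | 268 |

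Multiplying by 1.1 is the lenient convention: 10% lost from 260 leaves 234, short of 236. Dividing by 0.9 gives 334–338 and 264–268.

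**3. Other ways to reach 236**

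- *Unequal allocation.* At the most efficient ratio the one-sided unpooled total is (1.645 + 0.842)² × (√0.1875 + √0.24)² / 0.15² = 234.05. With dropout that is 257.5 (× 1.1) to 260.1 (÷ 0.9).
- *Continuity correction or Fisher's exact test.* With dropout by ÷ 0.9: 366–368 two-sided and 294–296 one-sided.
- *236 per arm.* Two-sided power would be 0.90–0.94, which does not match 0.8.

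**4. Power if 236 is the total** (1:1, exact binomial enumeration)

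| Reading | Rates, n per arm | Pooled z: two-sided / one-sided | Unpooled z: two-sided / one-sided |
|---|---|---|---|
| 236 randomised, 10% counted as non-responders | 22.5% vs 36.0%, 118 | 63.2% / 74.3% | 63.8% / 74.7% |
| 236 randomised, 10% excluded | 25% vs 40%, 106 | 64.9% / 75.6% | 65.4% / 76.1% |
| All 236 evaluable | 25% vs 40%, 118 | 69.6% / 80.0% | 70.2% / 80.3% |

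The first row uses 0.9 × 25% = 22.5% and 0.9 × 40% = 36.0%. If half of the dropouts still yield a stage at the planned rates (an assumption: 23.75% vs 38.0%), pooled power is 66.5% / 77.3%. At 2:1 in either direction, over both dropout readings, it is 57–61% / 69–72%.

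**5. If 236 is the evaluable number**

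The randomised target is 236 × 1.1 = 259.6, so 260, or 118 / 0.9 = 131.1, so 132 per arm and 264. One-sided pooled power is 79.6% at 260 and 80.0% at 264 with dropouts excluded. It is about 78% at either size with dropouts as non-responders.

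**6. Background rates (separate from the 236 calculation)**

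One-third and two-thirds of a cohort cannot both be 90 patients. Equal groups give (25 + 43) / 2 = 34%. A one-third/two-thirds split gives 25/3 + 43 × 2/3 = 37%. The text says about 35%.

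**The case against.** The best defence is that 236 is a correct number with a poor description: one-sided at 0.05, unpooled, 118 evaluable per arm. In a phase II trial exploring a regimen, a one-sided test is arguable, and the shortfall after dropout is then only about 4–6 points. The larger loss of 15–17 points depends on a two-sided test that the plan never specifies. This limits what can be said about size, and 63% should not be reported as the established power. It does not rescue the sentence, because no section states a one-sided test and the same sentence lists the 10% dropout as an input.

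A second point is that 236 does not identify its own origin. Two-sided unpooled at 25% vs 42% also gives 236 before dropout (117.08, so 118 per arm). Two-sided 25% vs 43% with dropout gives about 231–240, and 43% is the YWHAB-low rate in the same section. The text reads as a translation, so a mis-transcribed input is possible. That stands as a caution about origin. Both alternatives contradict the stated 40%, so a correction is needed in any case.

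Third, ITT in section 8.1 with the denominator rule in section 6.2 most naturally means that unstaged patients count as failures, which favours the lower power figures. That is a fair reading, but the plan does not say it, so both readings are shown.

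Finally, the background rates are all approximate, and 34% is close to 35%. What remains is the conflict between the fractions and the two equal counts. It is minor.

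**Conclusion.** The concern holds. At 25% vs 40%, alpha 0.05, power 0.8 and 10% dropout, the required total is 330–338 two-sided or 260–268 one-sided, for an uncorrected z-test at 1:1. The other tests and allocations tried do not bring the requirement, with dropout included, down to 236.

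If 236 is the total, 80% power is reached at 1:1 only with a one-sided test and all 236 evaluable, which leaves nothing for the plan's own dropout. If 236 is the randomised total, power is about 63–65% two-sided or 74–76% one-sided. If it is the evaluable number, the randomised target is missing. Which case applies cannot be settled from the document. The arithmetic mismatch is certain; the size of the shortfall depends on the unstated sidedness, allocation and dropout handling.

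**What to change.** In section 8.5, with matching text in section 8.3, state the between-group test for the primary endpoint, its sidedness, the allocation ratio, and how patients without a ypTNM stage count in the ITT analysis. State also whether 236 is a total, and whether it is randomised or evaluable. Then:

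- **(a) If 236 is the randomised total,** replace the claimed 0.8 with the power it delivers under those choices: about 63–65% two-sided or 74–76% one-sided for a pooled z-test at 1:1. No extra patients are needed.
- **(b) If 236 is the evaluable number,** say so, state that the test is one-sided, and give the randomised target of about 260–264 (264 if dividing by 0.9). That is 24–28 above 236. If unstaged patients are to count as non-responders, note that power at that target is about 78%.

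If the sponsor prefers to keep 0.8 with a two-sided test, or finds that an input was mis-transcribed, the input or the size should be corrected and the calculation rerun.

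Reconcile the one-third and two-thirds fractions with the two counts of 90 and with the overall 35%; the document does not show which figure is wrong.

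The cost is a rewording of sections 8.5 and 8.3, submitted to the ethics committee under the amendment procedure in section 13.

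### Section 8.5 lists a 10% dropout rate without saying how it fits an all-randomised primary analysis; if 25% and 40% are operated-patient rates, conventional inflation gives slightly under 0.80 power

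*Combined protocol and SAP*

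**What the plan says.** Section 8.5 gives the planning inputs. YWHAB-high patients on mFOLFOX6 alone "achieved a tumor downstaging rate of about 25" per cent. The expected rate with the flavonoid tablets added to "neoadjuvant chemotherapy is 40" per cent. The remaining inputs are given as "with a significance level of 0.05, an efficiency of 0.8, and a dropout rate of 10" per cent, where efficiency is read as power, and the stated total is 236. The section does not give sidedness, allocation ratio or test. Nor does it say what a dropout is, how the 10% entered the total, or whether 25% and 40% apply to all randomised patients or only to those operated on.

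Three other places govern how such a patient would be analysed:

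- Section 2.3 defines the primary endpoint by the pathological stage of the surgical specimen.
- Section 8.1 defines the ITT set as everyone randomised, analysed as assigned. It says of it "This analysis set is the main analysis set for" efficacy endpoints.
- Section 6.2 states: "Subjects who did not meet the primary endpoint criteria are included in the denominator but not in the numerator".

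Section 8.3 names no between-group test for the primary endpoint and no rule for missing specimens.

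**The concern.** A separate dropout rate in a sample size calculation normally means that dropouts contribute no outcome: the number of evaluable patients is divided by one minus the dropout rate, and the planned rates apply unchanged to those who remain. An all-randomised analysis in which patients without a specimen stay in the denominator works differently. It loses no patients, but it lowers both rates and shrinks the difference between them. Dividing by 0.90 does not correct for that.

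At stake are the stated power and the effect the primary analysis will estimate. The point also bears on how 8.5 is repaired: if the total were corrected simply by applying the usual inflation to 25% against 40%, this mismatch would remain.

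**Working it through.** **Inputs.** From 8.5: rates 0.25 and 0.40, alpha 0.05, power 0.80, dropout d = 0.10. Assumed because the plan is silent: 1:1 allocation, a two-proportion z-test with pooled null variance, and both one- and two-sided alpha.

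**Formulas.** With p̄ = (p1 + p2)/2, A = √[2p̄(1 − p̄)] and B = √[p1(1 − p1) + p2(1 − p2)]:

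- n per arm = (z_α·A + z_β·B)² / (p2 − p1)²
- power = Φ{[(p2 − p1)·√n − z_α·A] / B}

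**1. The plan's own figure.** For 0.25 and 0.40, A = 0.6624 and B = 0.6538.

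- Two-sided: n = 151.9, so 152 per arm (304). With dropout, 152/0.9 gives 169 per arm (338).
- One-sided: n = 119.5, so 120 per arm (240). With dropout, 120/0.9 gives 134 per arm (268).

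Neither inflated total is 236. Other variants with dropout included also miss it: unpooled variance gives 334 (two-sided) or 264 (one-sided), and continuity correction gives 368 or 296. Allocations of 1:2, 2:1 and 1:3 give 266 or more even before dropout. The exact match found is one-sided, unpooled and with no dropout: (1.645 + 0.842)² × (0.25×0.75 + 0.40×0.60)/0.15² = 117.5, so 118 per arm, total 236. So 236 appears to contain no dropout allowance.

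**2. Rates analysed if 10% have no specimen and count as failures.** Take 25% and 40% as operated-patient rates, with dropout equal in both arms and unrelated to response. Then 0.25 × 0.90 = 0.225 and 0.40 × 0.90 = 0.360, a difference of 0.135 instead of 0.150.

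**3. Power at the conventionally inflated total.** For 0.225 and 0.360, A = 0.6433 and B = 0.6362.

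- Two-sided, 169 per arm: (0.135 × 13 − 1.96 × 0.6433)/0.6362 = 0.777, so power is 0.781. Removing dropouts from the analysis would give 0.801. Reaching 0.80 with failure counting takes 178 per arm (356).
- One-sided, 134 per arm: power 0.786. Reaching 0.80 takes 140 per arm (280).

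With inflation matched to dropout (two-sided), power is 0.791 at 5%, 0.781 at 10%, 0.772 at 15% and 0.762 at 20%.

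**4. When the loss disappears.**

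- If 25% and 40% already count patients without a specimen as failures, power at 338 is 0.841 two-sided.
- If the total is inflated for 10% but only 7% lack a specimen, power at 338 is 0.800; if 5% lack one, it is 0.812.

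**5. Power at the planned 236 (118 per arm).**

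| Basis | Two-sided | One-sided |
|---|---|---|
| 25% and 40% are per randomised patient | 0.694 | 0.796 |
| 10% removed from the analysis | 0.648 | 0.757 |
| 10% counted as failures | 0.627 | 0.739 |

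Counting dropouts as failures instead of removing them costs 0.648 − 0.627 = 2.1 points two-sided, or 0.757 − 0.739 = 1.8 points one-sided. The total shortfall from 0.80 is 17.3 or 6.1 points, so most of it comes from the total of 236.

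**The case against.** The strongest objection is that the premise is not written down. A reader might infer from the listed dropout rate that the sponsor divided by 0.90 on the footing that dropouts leave the analysis. The documents do not support that: 8.5 does not say how the 10% was used, and 236 matches a calculation without it. The totals of 338 and 268 appear nowhere in the plan. This stands, and it is why the point concerns what 8.5 leaves undefined and what a conventional repair would do.

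A reader might also say that the plan expressly scores dropouts as failures. It does not. The sentence in 6.2 names neither dropouts nor missing specimens, and it follows the list of response categories. The reading is still the natural one: a patient with no specimen cannot have a ypTNM 0-I specimen, ITT keeps that patient, and no other rule is given.

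Nor is a dropout necessarily a patient without a specimen. Section 4.1 lets patients who progress, or who cannot tolerate the planned cycles, go to surgery, and they can have a ypTNM result. If 3 in 10 dropouts reached surgery and responded at the same rates, 7% would lack a specimen and the shortfall at 338 would vanish. On the other side, section 3.3 includes withdrawal of consent with refusal of follow-up, loss of contact and death, any of which can leave no specimen.

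Finally, the loss is small beside other uncertainties. At 152 per arm, two-sided, a control rate of 25.5% against 40% already gives 0.771. Adding a continuity correction moves the inflated total from 338 to 368, more than the move from 338 to 356 here. That is fair as to size. It does not remove the need to say which rates 8.5 describes, because on either basis a separate 10% inflation does not fit the stated analysis.

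**Conclusion.** The point holds in a limited, conditional form. A 10% dropout allowance applied to undiluted rates of 25% and 40% does not fit an all-randomised analysis in which patients without a specimen count as not downstaged. If those rates are per operated patient and 10% of each arm have no specimen, independently of response, the analysed difference is 13.5 points, and a conventionally inflated total has about 0.78 to 0.79 power. If the rates are already per randomised patient, there is no loss and the allowance is unnecessary.

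It would be going too far to conclude that dropout handling by itself defeats the stated power of 0.8. The effect is about 2 points, rests on an unstated basis for the rates, and shrinks if early stoppers still have surgery. The larger problem in 8.5 is that 236 does not follow from its inputs. All figures assume 1:1 allocation and a pooled z-test.

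**What to change.** In section 8.5:

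- State the sidedness, allocation ratio and test.
- Define a dropout as a randomised patient with no ypTNM result.
- State whether 25% and 40% are rates per randomised or per operated patient.
- Base the calculation on the all-randomised rates, with no separate inflation. If the rates are per operated patient and 10% is the expected share without a result, these are 22.5% and 36.0%. If they are already per randomised patient, keep 25% and 40%.
- Restate the power at the total the sponsor keeps.

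In section 6.2, say explicitly that a randomised patient without a ypTNM result is counted as not downstaged, if that is the intention.

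The cost is a few sentences and no extra patients, and it can be done together with correcting the derivation of 236. The restated power may be much less favourable than 0.8. At 236 it is about 0.63 two-sided or 0.74 one-sided with 10% counted as failures, and about 0.69 or 0.80 if the rates are already per randomised patient. Most of any fall comes from the total of 236 and only about 2 points from the failure counting.
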